# 2.3 Secondary Objectives

- Determine the effect of ESPB on emergency department (ED) operations metrics (disposition, length of stay, return to ED)
- Determine the effect of ESPB on use of opioid medications in the ED and during the follow up period
- Estimate rate of complications for ESPB when performed by EPs

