#### 3.6 Outcomes

#### 3.6.1 Primary Outcome and rationale

The primary outcome will be the proportion of patients receiving a second parenteral pain medication in the ED after a single-shot ESPB is performed by a study investigator. We have reviewed historical data that suggests that the rate of response (percentage of patients that do not require a second parenteral pain medication) in patients with urolithiasis, and who receive a parenteral medication as the first analgesic in the ED (approximately 70% of all kidney stone patients), ranges from 47 to 57% for the years 2020 – 2022. The average response rate is 53.4% during this period which is in line with historical trends prior to the Covid-19 pandemic.

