#### 3.6.3 Exploratory Outcomes

- Difference in highest and lowest pain scores while patient is in the ED
- Opioid pain medication usage measured in intravenous morphine equivalents and proportion of patients that receive a prescription for opioid pain medication
- Immediate complications of ESPB
- Survey follow-up administered online with/without telephone assistance at 1, 7 and 30 days from initial ED visit assessing the following outcomes:
  - Duration of pain control after ESPB (day 1 survey only)
  - o Delayed complications of ESPB (optional except for day 30)
  - Patient satisfaction with pain control and procedure
  - Use of opioid and other pain medication after discharge from the index ED visit

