#### 4.2 Inclusion Criteria

- Adult (>18 years) emergency department patient presenting with pain due to uncomplicated urolithiasis
- Imaging confirmation of urolithiasis on the index encounter or prior encounter within 7 days
- Patient received one dose of parenteral pain medication in the ED

Rationale for inclusion criteria: We seek to enroll adult patients who have pain that initially required parenteral medications to treat and thus, may benefit from adjunct therapy to treat severe kidney stone related pain.

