# 4.4 Selection of external control patients

External control patients will be selected from a population of patients meeting the following criteria: 1) adult ED patient with the diagnosis of uncomplicated kidney stones; 2) received at least one dose of parenteral medication while in the ED; 3) presentation to the ED between 7/1/2021 and the study start date. From this population, propensity score matched control patients will be selected at a ratio of 3 controls to 1 ESPB patient. External control population patients are not active patients in this study and analysis of their data will be secondary use of data collected during routine care. To provide valid comparison between control patients and ESPB patients, we will compare pain scores obtained by the treatment team (bedside nurse). For all other primary and secondary outcomes, data collection utilizes EHR query that does not require prospective data collection. Please see the data collection section of this protocol for further details.

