# 6.4 Secondary data collection from the EHR

Variables regarding patient demographics, ED operations metrics, diagnoses, medical history, procedures performed, other healthcare encounters, nurse assessments of pain, medications administered, and prescriptions provided during the index ED visit will be obtained using direct query to the EHR databases (RDW, HSDW, Caboodle, Clarity) and confirmed with manual chart review if needed. Using the same EHR query we will also collect data regarding historical control patients (external controls that did not receive ESPB). Control patient data will be collected as secondary data collection of routinely collected health information.

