#### 7 DATA ANALYSIS PLAN

# 7.1 Descriptive analysis and statistical testing

The primary exposure of interest is performance of ESPB for uncomplicated renal colic in the ED. We will describe the center and spread for all collected variables. Additionally, we will compare data from participants to historical control patients whose data is collected secondarily from query to the EHR. Continuous variables will be described by medians with interquartile ranges and differences will be assessed by two-sample t-test or Wilcoxon's rank sum test depending on distribution. Categorical variables will be described by counts with proportions and differences assessed using the Chi-squared test or Fisher's exact test where appropriate. An alpha = 0.05 will be considered the level of significance in all analyses.

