#### 7.4 Other outcomes

Other outcomes unique to study patients (received ESPB as part of this study) including change in pain score, follow up assessment outcomes, complications, and patient satisfaction will be analyzed before-after the ESPB, change over time, or descriptively as appropriate. Secondary outcomes derived from EHR query (ED operations metrics, opioid medication usage and prescriptions) will be analyzed for study patients in comparison to external controls. All comparisons to external control patients will be made using data collected via EHR query rather than prospectively collected data (investigator collected pain scores, patient satisfaction, follow survey results, etc.) which will be reported descriptively and without comparison to controls.

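### The ED opioid outcome has no stated time window and, on its natural reading, includes the qualifying dose, whose amount the planned two-sample test does not adjust for

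*Combined protocol and SAP*

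**What the plan says.** - **Outcome.** Section 3.6.3 (and 2.9) lists "Opioid pain medication usage measured in intravenous morphine equivalents and proportion of patients that receive a prescription for opioid pain medication". This gives a unit but no window.
- **Objective.** Section 2.3: "Determine the effect of ESPB on use of opioid medications in the ED and during the follow up period". The ED part is not tied to the time of the block.
- **Data.** Section 6.4: "medications administered, and prescriptions provided during the index ED visit will be obtained using direct query to the EHR databases". This is the only window given for administered drugs.
- **Entry.** ESPB patients: "Patient received one dose of parenteral pain medication in the ED" (4.2). External controls: "received at least one dose of parenteral medication while in the ED" (4.4). Neither restricts the drug class. Section 3.1 names both opioids and NSAIDs as the usual parenteral drugs.
- **Comparison.** Section 7.4: "opioid medication usage and prescriptions) will be analyzed for study patients in comparison to external controls". For continuous variables 7.1 says "differences will be assessed by two-sample t-test or Wilcoxon's rank sum test depending on distribution".
- **Matching.** The propensity model in 7.2 includes initial pain medication type. It does not include the amount given.
- **Contrast.** The primary outcome does have an anchor: "receiving a second parenteral pain medication in the ED after a single-shot ESPB is performed" (3.6.1).

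**The concern.** An ESPB patient's qualifying dose is given before the block, so it is a baseline value. If it is counted in the outcome and not adjusted for, two things follow. Its spread between patients adds noise to a comparison that it cannot inform. And any difference between the groups in its size is added to the apparent block effect. The second matters because the controls are historical (7/1/2021 to study start, section 4.4), while 3.1 describes recent efforts to cut ED opioid use. First-dose amounts could have drifted over that time.

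Opioid use is one of the stated secondary objectives and part of the rationale for the block, so a real reduction could be blurred. The information needed to avoid this is in data that the study already plans to extract.

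**Working it through.** **The plan's own figures.** The documents give no SD, effect size, opioid share or power for opioid use, so nothing can be reproduced for this outcome. The one related design figure, Simon's 18/54, does reproduce: p0 = 0.55, p1 = 0.75, alpha 0.05 and beta 0.10 give n1 = 18, r1 = 10, N = 54, r = 35, exact alpha 0.0477 and power 0.9007. It concerns the primary response proportion and says nothing about opioid use.

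**Inputs.** From 2.10: 60 ESPB patients and up to 180 controls. From 7.1: alpha 0.05, taken as two-sided (assumption). Base power of 80%: assumption.

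**1. Gain from adjustment.** Let r be the correlation between first-dose morphine equivalents and the analysed outcome. Adjustment multiplies the residual variance by 1 − r². If the unadjusted test has 80% power, the adjusted power is Φ(2.802/√(1 − r²) − 1.960).

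| r (assumed) | 1 − r² | Power |
|---|---|---|
| 0.1 | 0.99 | 80.4% |
| 0.3 | 0.91 | 83.6% |
| 0.5 | 0.75 | 89.9% |

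The detectable difference without adjustment is 2.802 × √(1/60 + 1/180) = 0.418 SD. At r = 0.5 it is 0.418 × √0.75 = 0.362 SD.

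**2. Loss from counting the first dose unadjusted.** Now let k = SD(first dose)/SD(later use) and c = the correlation between first dose and later use, both assumed. The SD of the total is √(1 + k² + 2ck) in units of the later-use SD. Set the effect so that later use alone has 80% power (0.418 SD). Power on the unadjusted total is then:

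| k | c = −0.3 | c = 0 | c = 0.3 |
|---|---|---|---|
| 0.25 | 83.5% | 77.6% | 72.0% |
| 0.5 | 82.0% | 70.7% | 61.4% |
| 1.0 | 65.8% | 50.8% | 41.2% |

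The loss vanishes only if larger first doses go with clearly less later use (c below −k/2). Steps 1 and 2 agree: with c = 0, r = 0.5 corresponds to k = 0.58, and 1 + 0.58² = 1.33 = 1/0.75.

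**3. Does matching on type already deal with it?** A simulation (2,000 runs) assumed exact matching on opioid versus non-opioid start, first doses of 2 to 8 mg, a later parenteral drug in 45% v 25% (the complements of 55% and 75%), 70% of those drugs opioid, and first dose independent of later use. Type explained 82%, 76% and 66% of first-dose variance when 30%, 50% and 70% of starts were opioid.

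| Analysis | 30% | 50% | 70% |
|---|---|---|---|
| t-test, total | 22% | 17% | 19% |
| Total adjusted for type | 42% | 39% | 33% |
| Total adjusted for amount | 49% | 48% | 46% |
| t-test, later use only | 49% | 48% | 46% |

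These inputs lie at the large end of step 2. Mean later dose is 4.8 mg and mean square 27.2, so control later-use variance is 0.315 × 27.2 − (0.315 × 4.8)² = 6.28 (SD 2.51). First-dose SD is 2.23 to 2.52, so k is about 0.9 to 1.0. The ordering of the rows is informative; the absolute powers are illustrative.

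**4. Total or later use?** Total = first dose + later use. In a linear model with the first dose as a covariate, changing the outcome from later use to total raises the first-dose coefficient by 1 and leaves the treatment coefficient unchanged. This identity does not carry over to rank-based or two-part models.

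**The case against.** - **The plan never says that a total is compared.** A reader might infer that the protocol prescribes a total including the qualifying dose. It does not; it neither includes nor excludes that dose. What stands is that the window is undefined and that 2.3 and 6.4 together point to the whole visit.
- **The first dose is not ignored.** A reader might infer that nothing accounts for it. In fact initial medication type is in the propensity score, along with first pain score and triage acuity, so the main contrast (opioid or non-opioid start) is partly balanced. This stands. What is left is imbalance in amount within type, and a test that does not turn the balance into precision.
- **Many first doses may add nothing.** An NSAID start contributes zero morphine equivalents, and the opioid share is unknown. This stands, although a mix of zeros and positive doses is itself variation that the block cannot affect.
- **The power figures are assumptions.** This stands too. At r = 0.1 the gain is negligible, and with negative c the loss can reverse. Normal theory also fits poorly: 53.4% of historical patients had no second parenteral drug (2.10), so later use will contain many zeros.
- **Total exposure is a legitimate measure.** Section 8.4 names lower total exposure to other pain drugs as a possible benefit. This is a reason to keep reporting the total, but not to leave the baseline dose unadjusted: by step 4, the linear adjusted estimate is the same for either outcome.
- **Stakes.** Section 3.6.3 calls the outcome exploratory. A reader might infer that the trial is underpowered for opioid use, but no power was claimed for it.

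**Conclusion.** The point holds as a modest improvement to the analysis; it does not threaten the trial's main conclusion. The opioid outcome lacks a window. Its natural reading includes a dose that the block cannot change, and the amount of that dose is adjusted for nowhere. Matching on type helps with balance but leaves amount within type open, and the unadjusted test does not use it for precision.

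The gain is between nothing and worthwhile: from an assumed 80%, to about 80%, 84% or 90% at r = 0.1, 0.3 or 0.5. The base power and the correlations are assumptions, and the documents support no single figure.

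A reader might also infer that moving the clock or adjusting makes the groups comparable. It does not. ESPB patients must reach the block after one dose, while controls need at least one and have no block time, so the fix below does not remove bias from this difference.

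**What to change.** 1. In 3.6.3 and 7.4, state the window of the ED opioid outcome, with the same time zero in both groups: the first parenteral pain medication, since controls have no block time. Section 4.4 says only parenteral medication, so spell this out for controls.
2. In 7.4, replace the two-sample test for this outcome with a regression that adjusts for the morphine equivalents of the first parenteral dose (0 if non-opioid) and respects the 3:1 matching. Use a robust or rank-based version if the outcome is skewed, or a two-part model if many values are zero. Choose the form before the comparison is run.
3. Report total ED opioid use alongside.
4. Give the outcome one label: 3.6.3 calls it exploratory, while 2.3 and 7.4 treat it as secondary.
5. State as a limitation that pre-block time and the different dose-count conditions in 4.2 and 4.4 remain.

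**Cost.** Wording in the analysis plan, and a regression in place of a simple test. The 6.4 query already covers administered medications; confirm that it returns dose and time. No new patient contact is needed.

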#### 4 STUDY POPULATION AND ENROLLMENT

#### 4.1 Target Population

Our target population is patients who present to the U-M Adult ED with flank or back pain due to uncomplicated urolithiasis (see also appendix figure 1A).

#### 4.2 Inclusion Criteria

- Adult (>18 years) emergency department patient presenting with pain due to uncomplicated urolithiasis
- Imaging confirmation of urolithiasis on the index encounter or prior encounter within 7 days
- Patient received one dose of parenteral pain medication in the ED

Rationale for inclusion criteria: We seek to enroll adult patients who have pain that initially required parenteral medications to treat and thus, may benefit from adjunct therapy to treat severe kidney stone related pain.

#### 4.3 Exclusion Criteria

- Pregnancy or breastfeeding
- Prisoner or incarcerated individual
- Therapeutic anticoagulation or coagulopathy.
- Active treatment for urinary tract infection (either acute infection or chronic therapy)
- Prior spinal surgery in the thoracic region
- Allergy to local anesthetic or prior local anesthetic systemic toxicity
- Covid positive
- Inability to communicate verbally or read/write in English
- Currently taking strong CYP1A2 inhibitor (fluvoxamine, amiodarone, fluoroquinolones, etc.)
- Glucose-6-phosphate dehydrogenase deficiency

Rationale for exclusion criteria: Pregnant patients are especially at risk for complications of urolithiasis as are patients with active treatment for acute UTI or chronic suppressive therapy and will be excluded from this study. Long-acting local anesthetics (Ropivacaine) has not been well studied in lactating patients or infants and thus patients who are actively breastfeeding will be excluded. Prior spinal surgery in the anatomic region of the ESPB may distort anatomy and increase risks of performing this procedure. Patients with prior local anesthetic toxicity or allergy to local anesthetics will also be excluded. Patients who cannot communicate in English will be excluded due to difficulty in obtaining informed consent and difficulty following instructions during positioning for the procedure. Covid-19 positive patients will be excluded for infection prevention and safety of study team members. CYP1A2 strong inhibitors such as fluvoxamine, fluoroquinolones or amiodarone can lead to delayed metabolism of ropivacaine. Finally, patients with G6PD may develop methemoglobinemia after administration of local anesthetics.

# 4.4 Selection of external control patients

External control patients will be selected from a population of patients meeting the following criteria: 1) adult ED patient with the diagnosis of uncomplicated kidney stones; 2) received at least one dose of parenteral medication while in the ED; 3) presentation to the ED between 7/1/2021 and the study start date. From this population, propensity score matched control patients will be selected at a ratio of 3 controls to 1 ESPB patient. External control population patients are not active patients in this study and analysis of their data will be secondary use of data collected during routine care. To provide valid comparison between control patients and ESPB patients, we will compare pain scores obtained by the treatment team (bedside nurse). For all other primary and secondary outcomes, data collection utilizes EHR query that does not require prospective data collection. Please see the data collection section of this protocol for further details.

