# 2.10 Sample Size

- This study is a two-stage trial with one planned interim analysis for futility
- Based on the prior 30-month time period (as of May 2022), 572 out of 1071 patients (53.4%) presenting to the ED and meeting the inclusion criteria did not require a 2nd parenteral pain medication during the ED encounter. Thus, we estimate a baseline response rate of 55%.
- Prior work by Nobel et al.¹and Aydin et al.² suggests that no patient will require a second dose of any pain medication after ESPB, but we estimate a conservative response rate of 75% for treatment with ESPB.
- Using Simon's optimal two-stage design with these parameters and  $\alpha$  = 0.05,  $\beta$  = 0.10, we estimate that 18 subjects will be required at the interim analysis and 54 subjects will be required to complete this study.
- Using a Bayesian two-stage design, where interim analysis is planned at one-third total enrollment and a stopping rule if there is only a 10% probability of ESPB demonstrating a 75% response rate, we estimate that 45 total subjects (15 at interim analysis) will be required to achieve a 1.4% chance of stopping early and 95.2% chance of rejecting the null hypothesis.
- This study will aim to achieve a total enrollment of 60 subjects who receive ESPB to account for losses to follow up and withdrawals from the study. Up to 180 (3:1 ratio) historical controls will also be included in the study thus the total enrollment including both treatment and control patients is 240.

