# 4.6 Screening

- Study team members will screen for patients using the ED track board and other patient lists/reports within MiChart (EPIC EHR)
- Study team members will review potential subjects' presenting symptoms, prior medical history, and imaging findings
- Study team members will then notify a physician investigator on call of potential subjects currently in the ED
- Physician investigator will review inclusion and exclusion criteria with other study team members (if they did not perform screening personally) as well as the potential subject

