# 7.2 Primary analysis

Our primary analysis will evaluate the proportion of patients receiving ESPB who require a second parenteral pain medication. This outcome will be compared to external control patients who are selected using propensity score matching at a ratio of 3:1. The propensity score model will include the following variables: age, gender, triage acuity level (ESI score), first ED pain score assessed by nursing, Charlson Comorbidity Index, chronic and initial pain medication type. Data for this outcome will be collected via EHR query as above.

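### Section 4.4 defines the external control pool without the imaging confirmation (4.2) or the exclusions (4.3) that ESPB patients must satisfy, so the primary matched comparison can include controls who could not have entered the trial.

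*Combined protocol and SAP*

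**What the plan says.** **Controls.** Section 4.4 sets three criteria. The first two are "adult ED patient with the diagnosis of uncomplicated kidney stones; 2) received at least one dose of parenteral medication while in the ED". The third is "presentation to the ED between 7/1/2021 and the study start date". Matched controls are drawn from that population at 3 per ESPB patient. The section does not cite 4.2 or 4.3. It sends the reader to the data collection section for details.

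**ESPB patients.** Section 4.2 requires "Imaging confirmation of urolithiasis on the index encounter or prior encounter within 7 days" and a dose of parenteral pain medication. Section 4.3 adds ten exclusions. For two of them the stated reason is prognostic: "Pregnant patients are especially at risk for complications of urolithiasis as are patients with active treatment for acute UTI". Under 4.6, staff review each candidate's "presenting symptoms, prior medical history, and imaging findings".

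**Matching and data.** Section 7.2 makes the matched controls the comparator for the primary outcome. Its propensity variables are "age, gender, triage acuity level (ESI score), first ED pain score assessed by nursing, Charlson Comorbidity Index, chronic and initial pain medication type". Section 6.4 uses one EHR query for both groups and lists the variables to be collected.

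**The concern.** An external-control comparison is easiest to defend when both groups pass the same entry rules before any matching. Here the ESPB group passes a diagnostic and exclusion screen that the control pool does not. Matching balances only the variables in its model and does not remove patients who fail an entry rule. If patients without imaging confirmation, pregnant patients or patients under treatment for UTI need a second parenteral dose more or less often than eligible patients, the matched control rate moves for reasons unrelated to the block.

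The wording also leaves a choice open. Two analysts could build different control groups from it, one applying 4.2 and 4.3 and one not, and the choice could be made after the ESPB outcomes are known.

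**Working it through.** This is mainly a comparison of text.

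**1. Entry rules side by side**

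| Requirement | ESPB patients | Controls (4.4) | In the 7.2 model? |
|---|---|---|---|
| Uncomplicated stones | Yes (4.2) | Yes | n/a |
| Imaging at index or prior encounter within 7 days | Yes (4.2) | Not stated | No |
| Parenteral dose | Pain medication (4.2) | At least one parenteral medication | Initial pain medication type |
| Not pregnant | Yes (4.3) | Not stated | No |
| No active UTI treatment, acute or chronic | Yes (4.3) | Not stated | No |
| Other 4.3 exclusions | Yes | Not stated | No |

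The missing word *pain* in 4.4 is probably shorthand, and matching on initial pain medication type largely covers it.

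**2. Does other text supply the missing rules?**
- Section 6.4 lists diagnoses, medical history, medications and other fields, but sets no eligibility filter for controls.
- *Uncomplicated* is not defined. Section 4.2 uses the same word for ESPB patients, and the plan still adds imaging and the exclusions for them.
- Section 4.1 points to Figure 1A for eligibility. It is not shown in the text reviewed and could not be checked.

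**3. Which exclusions could matter for the outcome?** The 4.3 rationale ties pregnancy and UTI treatment to complications of stones, not to analgesic need. Six others are explained by safety of the block or drug (thoracic spinal surgery, local anesthetic allergy or toxicity, CYP1A2 inhibitors, G6PD deficiency), by consent and positioning (English), or by infection prevention (Covid). No rationale is given there for anticoagulation or incarceration. No section links imaging status or any exclusion to the need for a second dose.

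**4. Size**
- Let *f* be the share of matched controls who are ineligible, and *q* their response rate (no second parenteral dose).
- With eligible controls at the 55% baseline in 2.10, the control rate is 0.55 − *f*(0.55 − *q*).
- The documents give neither *f* nor *q*. Purely as an assumed range, take *f* from 5% to 30% and *q* from 25% to 65%.
- Lowest control rate: 0.55 − 0.30 × 0.30 = 46%. Highest: 0.55 + 0.30 × 0.10 = 58%.
- At *f* = 5%, the shift is 0.05 × 0.30 = 1.5 points down to 0.05 × 0.10 = 0.5 points up.
- If *q* = 55%, the shift is zero at any *f*.

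The range shows that either direction is possible and that the size depends entirely on two unknowns. It is not an estimate.

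**The case against.** The strongest reply is that 4.4 is shorthand. Section 8.6.1 says the study involves adults who meet the inclusion and exclusion criteria, and 2.10 counts controls within the total enrollment of 240. Read together, these could apply eligibility to everyone. That reading is possible but not secure, because 4.4 says that controls are not active patients in the study. Figure 1A might also settle the matter. Even so, 4.4 is the operative rule and would need to agree with it.

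A second reply is that no consequence is shown. Most of this stands. Restricting to uncomplicated stones may already remove some infected or pregnant patients. Most exclusions have no evident bearing on analgesic need. Age, gender, acuity, pain score and comorbidity may partly balance related risk.

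Two stronger readings are tempting, and the documents support neither. A reader might infer that the comparison is biased in favor of the block. No passage gives the share of ineligible controls or how their response differs, so even the sign is unknown. A reader might also infer that the control pool is looser than the cohort behind the planning rate, because 2.10 describes "572 out of 1071 patients (53.4%) presenting to the ED and meeting the inclusion criteria". That rate reproduces (572/1071 = 53.4%), but 3.6.1 describes the same 53.4% cohort by urolithiasis and a parenteral first analgesic, without mentioning imaging. Whether that cohort was filtered on imaging is unclear, so no contrast with it should be drawn.

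**Conclusion.** The point holds as a gap between stated rules. As written, 4.4 admits controls who could not have entered the trial; neither 7.2 nor 6.4 removes them; and they would sit in the comparator for the primary outcome. The effect on the result cannot be derived and may be close to nil. No stated figure in the plan is wrong, and the design sizes (18 and 54 for the Simon design, 60 and up to 180 for enrollment) are unaffected.

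The conclusion rests on reading 4.4 as the complete control rule and on Figure 1A not adding to it. It is a cheap improvement of low to moderate severity, worth making because it aligns the two groups and removes an analyst's choice.

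**What to change.** Amend 4.4 so that, before matching and before outcomes are compared, each control must:

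- (a) have imaging confirmation of urolithiasis at the index encounter or a prior encounter within 7 days, as in 4.2. Keep the reference to a *prior* encounter, so that imaging after the visit does not qualify;
- (b) have received at least one dose of parenteral *pain* medication. Keep *at least one*, because limiting a control's whole visit to one dose would select on the outcome;
- (c) have none of the 4.3 exclusions that can be established from the EHR query or the chart review allowed in 6.4, at minimum pregnancy and active UTI treatment.

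List the exclusions that cannot be established, and make Figure 1A agree if it covers controls.

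**Cost.** Protocol wording, plus filters on a query that is already planned. Imaging results are not named in 6.4 and may need an added field or chart review. Medications there are those given or prescribed at the index visit, so chronic UTI therapy may need the medical history field or chart review. The pool will shrink somewhat. Taking the 2.10 count at face value, 1071/30 = 35.7 patients per month, so 180 controls equal about 180/35.7 = 5.0 months of such patients before exclusions and matching. The study start date is not in the text, so the actual pool cannot be counted here.

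The change aligns who is eligible, not when eligibility is judged: a control could still have been imaged after a second dose. That limit should be stated when the results are reported.
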